15.2.3. WOUND AREA REDUCTION RATE (UNIT: %)

Define: wound area change over 14 days or until deemed ready for closure by investigator (whichever occurred first).

Formula: wound area reduction rate = (wound area before study treatment –wound area after study treatment 14 days or deemed ready for closure before 14 days)÷wound area before study treatment×100%.

Measurement: 3D Wound Imaging System, the value for area can be collected from the 3D wound imaging system report directly.

Analysis Plan

Protocol No.: KCI.VERAFLO.2018.02

Evaluation time point: Day of Randomization (Day 0), Dressing Change Visit (s), and End of Treatment Visit

Statistical method:

Descriptive statistics of actual wound area and imputed wound area (LOCF and NOCB only) and wound area changes (wound area before study treatment –wound area of each visit) and wound area reduction rate at each visit (wound area before initial study treatment –wound area at each visit)÷wound area before initial study treatment×100%) by treatment group, visits and overall will be provided. Listings of actual wound area and its change will be presented and sorted by subject id, treatment group and visit.

An analysis of covariance (ANCOVA) model on mean change in actual wound area and imputed wound area reduction rate as dependent variables with treatment group, center and treatment-by-center interaction (if the interaction effect is not statistically significant, then it will be removed from the final model) as fixed factors, wound size (wounds surface area, <15cm² (ref), 15-30cm², and >30cm²) as covariate will be performed. The following statistics will be presented: LS Means, difference of the LS Means, as well as its 95% CI, p-value for LS Mean difference, p-value of treatment group, center, treatment-by-center interaction (present only if interaction effect is significant) and wound size. The FAS will be used for this analysis.

15.2.4. WOUND CLINICAL ASSESSMENTS

Define: Wound depth, edges, necrotic tissue type and amount, granulation tissue, undermining, exudate type and exudate amount of target wound after therapy will be evaluated.

Measurement: Wound depth, edges, necrotic tissue type and amount, granulation tissue, undermining, exudate type and exudate amount will be evaluated according to below table.

Wound Depth	1 = non-blanchable erythema on intact skin 2 = Partial thickness skin loss involving epidermis and/or dermis 3 = Full thickness skin loss involving damage or necrosis of subcutaneous tissue; may extend down to but not through underlying fascia; and/or mixed partial and full thickness and/or tissue layers obscured by granulation tissue 4 = Obscured by necrosis 5 = Full thickness skin loss with extensive destruction, tissue necrosis or damage to muscle, bone or supporting structures				
Edges	1 = Indistinct, diffuse, none clearly visible 2 = Distinct, outline clearly visible, attached, even with wound base 3 = Well-defined, not attached to wound base 4 = Well-defined, not attached to base, rolled under, thickened 5 = Well-defined, fibrotic, scarred or hyperkeratotic				
Necrotic tissue type	1 = None visible 2 = White/grey non-viable tissue and/or non-adherent yellow slough 3 = Loosely adherent yellow slough 4 = Adherent, soft, black eschar 5 = Firmly adherent, hard, black eschar				
Necrotic tissue amount	1 = None visible 2 = < 25% of wound bed covered 3 = 25% to 50% of wound covered 4 = > 50% and < 75% of wound covered 5 = 75% to 100% of wound covered				
Granulation Tissue	% change in granulation tissue from baseline by 3D Wound Imaging	1 = Skin intact or partial thickness wound 2 = Bright, beefy red; 75% to 100% of wound filled and/or tissue overgrowth 3 = Bright, beefy red; < 75% and > 25% of wound filled 4 = Pink, and/or dull, dusky red and/or fills ~ 25% of			

Analysis Plan

Protocol No.: KCI.VERAFLO.2018.02

	System	wound 5 = No granulation tissue present
Undermining	1 = None present 2 = Undermining < 2 cm in any area 3 = Undermining 2-4 cm involving ≤ 50% wound margins 4 = Undermining 2-4 cm involving > 50% wound margins 5 = Undermining > 4 cm or Tunneling in any area	
Exudate type	1 = None 2 = Bloody 3 = Serosanguinous: thin, watery, pale red/pink 4 = Serous: thin, watery, clear 5 = Purulent: thin or thick, opaque, tan/yellow, with or without odor	
Exudate amount	1 = None, dry wound 2 = Scant, wound moist but no observable exudate 3 = Small 4 = Moderate 5 = Large	

Evaluation time point: Day of Randomization (Day 0), Dressing Change Visit (s), End of Treatment Visit.

Statistical method: The descriptive statistics (frequency and percentage) of wound clinical assessments change from baseline (change scores from -4 to +4) will be summarized by treatment group, visit and overall. Listings will be presented and sorted by treatment group, subject id.

The Wilcoxon signed rank test and the Wilcoxon rank-sum test will be performed to detect significant changes from baseline within treatment group (p-values) or significant differences in change scores between treatment groups (p-values).

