### **5.5.2.2 Day of Randomization (Day 0)**

The following data will be collected:

- (1) Physical exam.
- (2) Wound clinical assessments

Wound depth, Edges, necrotic tissue type and amount, granulation tissue, undermining, exudate type and exudate amount will be evaluated.

For subjects who present with multiple wounds suitable for the trial, the wound with the greatest volume will be randomized.

- (3) Definitive surgical debridement (if applicable).
- (4) Digital/3D wound imaging

Digital photos and three-dimensional photographs will be taken of the wound (without dressing) for all subjects, and target wound length, width, depth, surface area and volume will be measured and reported.

When a wound extends over a convex/curved surface, such as a limb, the imaging will be taken so that each part of the wound is photographed (max. 2 photos) in a way that the photographed surface is as flat as possible in relation to the camera lens.

- (5) Evaluation of inclusion/exclusion criteria again.
- (6) Randomization

Subjects who continue to meet all inclusion and no exclusion criteria will be randomized in a 1:1 ratio stratified by wounds surface area (<15cm^2, 15-30cm^2, and > 30cm^2) to be treated with either investigational group [V.A.C. VERAFLTM Dressing Kit with ULTATM Therapy Unit (instillation) ] or control group [Negative pressure wound drainage material with Wall suction (without instillation)].

- (7) Administer assigned NPWT treatment

Date, time, condition and settings of NPWT treatment need to be recorded.

(8) Concomitant medications

All medications the subject is taking during the study.

(9) Collect and assess AEs/SAEs.

(10) Device deficiencies.

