### **Secondary and safety endpoints**

For other continuous secondary endpoints, the same analysis procedure will be conducted as above. In addition, Kaplan-Meier and log rank test will be performed for time to completion of wound bed preparation. An analysis of covariance (ANCOVA) model on mean change in wound area reduction rate as dependent variables with treatment group as fixed factors, site, treatment-by-site interaction (present only if interaction effect is significant) and wound size as covariate will be performed. The difference between the two treatment groups and 95% CI will be reported. The Wilcoxon rank-sum test and Wilcoxon signed rank test will be performed for wound clinical assessments.

In addition, all efficacy and safety endpoints will be summarized descriptively for subjects in each treatment group and overall. The continuous data will be summarized by number of subjects, mean, standard deviation (SD), median, minimum and maximum. The categorical data will be summarized by frequency counts along with associated percentages.

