15.2.2. TIME TO COMPLETION OF WOUND BED PREPARATION (UNIT: DAY)

Define: Duration from the randomization until target wound ready for closure by secondary intervention judged by the investigator.

Evaluation time point: Day of Randomization (Day 0) and End of Treatment Visit.

Measurement: the date deemed ready for closure by secondary intervention - the date of the randomization + 1.

Statistical method: the difference between investigational group and control group will be assessed by Kaplan-Meier method and log rank test, and with covariate adjustment using the Cox proportional hazard regression and Wald Chi-Square.

Censor data define: .

The duration of treatment for a patient is considered right-censored if it meets one of the below conditions:

- Patient completed the study but the completion category was “The treatment duration up to 14 Days”, and the subjects’ target wound not ready for closure before end of treatment visit. Patient’s will be censored on day of end of treatment visit.
- Patient prematurely withdraws from the study and the subjects’ target wound not ready for closure before end of treatment visit, patients will be censored on the date of their last 3D wound imaging assessment.
- Subjects with no post-baseline 3D imaging wound measurements assessments will be censored on the day of randomization (i.e. Day 0).

Here, duration of treatment for a patient is defined as the date of the last wound measurements assessments minus the date of randomization plus one.

The Kaplan-Meier analysis of the time to completion of wound bed preparation will be performed, the Kaplan-Meier plot will be presented. The Cox proportional hazard regression with covariates from primary endpoints will be used to estimate the hazard ratios for effect of treatment factor.

The results of the log-rank test for the comparison of investigational group and control groups will be expressed by a Chi-square statistic and P-value, The results of cox proportional hazard regression will be present by HR statistic and P value, the P-value <0.05 will be considered as statistically significant.

An example of SAS code for cox proportion regression model is provided:

```
Proc phreg;
Class treat(ref=control) center(ref=sitel1) woundtype(ref=1);
Model time*completion of wound bed preparation(yes) =treat center treat*center woundtype
/risklimits;
Run;
```

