15.4. SUMMARIES FOR SUBJECTS RECEIVED TREATMENT

The number of days subjects received treatment and number of dressing changes will be listed and summarized by treatment group. The Wilcoxon rank-sum test will be used to test the differences between two groups, p-value will be presented.

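### The between-arm rank-sum tests of the wound clinical assessments leave out the randomisation strata, which costs power if wound area predicts the change scores

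*SAP*

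**What the plan says.** Protocol 5.5.2.2 has eligible subjects "randomized in a 1:1 ratio stratified by wounds surface area", in three classes: below 15, 15 to 30 and above 30 cm². No other stratification factor is named in the documents.

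For the wound clinical assessments, Protocol 6.5.1 (under Secondary and safety endpoints) states: "The Wilcoxon rank-sum test and Wilcoxon signed rank test will be performed for wound clinical assessments". SAP 15.2.4 works with the change from baseline in each of eight five-level scores, so changes run from −4 to +4. Its sentence on testing begins "The Wilcoxon signed rank test and the Wilcoxon rank-sum test will be performed to detect significant changes from baseline within treatment group" and goes on to cover "significant differences in change scores between treatment groups (p-values". Only this second part, the rank-sum comparison between arms, is at issue here. Neither document names a stratum or covariate for it.

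Elsewhere the plan does use the area class. It is in the ANCOVA for volume (SAP 15.1.3) and for area (SAP 15.2.3), and in the exploratory mixed models for volume, area and granulation tissue (SAP 16). For time to completion of wound bed preparation, SAP 15.2.2 sets an unstratified log-rank test beside an adjusted model: "The Cox proportional hazard regression with covariates from primary endpoints will be used".

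SAP 15.4 treats days on treatment and number of dressing changes in the same unstratified way: "The Wilcoxon rank-sum test will be used to test the differences between two groups".

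**The concern.** Stratified allocation makes the arms nearly alike in their mix of area classes, so differences between classes add little to the real chance variation of the treatment comparison. The ordinary rank-sum test computes its variance as if allocation had been unrestricted, and so leaves the between-class variation in its error. If the classes differ in their change scores, that error is too large for the design. The test then rejects too rarely under the null and has less power than one that ranks within classes.

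At stake is the ability to see a difference on eight secondary scores. For seven of them the plan contains no area-adjusted analysis at all. The eighth, granulation tissue, has one only in the exploratory mixed model.

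**Working it through.** **1. The plan's own sample size.** SAP 5.4 gives margin 20, SD 40, one-sided alpha 0.025 and power 80%. With an assumed true difference of 0, the normal approximation is n = 2 × (1.96 + 0.8416)² × (40/20)² = 62.8, so 63 per arm. With the noncentral t distribution, power is 0.7952 at 63 and 0.8015 at 64 per arm. The stated 64 per arm is reproduced. It rests on the primary endpoint alone. The documents give no power, effect size or sample size for the clinical assessments.

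**2. Inputs for the comparison of tests.**

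- From the documents: 1:1 allocation within three area strata (Protocol 5.5.2.2), scores from −4 to +4 (SAP 15.2.4), two-sided 5% level (SAP 7.5), 64 per arm (SAP 5.4).
- Assumed, because the documents do not give them: permuted blocks of 4, a treatment shift of 0.5 within-stratum SD that is the same in every stratum, stratum shares of one third each or 10/20/70%, and a shift of b SD between adjacent area classes, with b from 0 to 1.

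The latent change is b × (class − 1) + 0.5 × arm + standard normal error, with class coded 0, 1, 2. It is rounded and limited to −4 to +4. For equal strata the share of latent variance explained by area is (2b²/3) ÷ (1 + 2b²/3). At b = 0.5, for example, this is 0.1667 ÷ 1.1667 = 14.3%.

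**3. The two tests.** For stratum k of size N_k, let T_k be the rank sum in one arm minus its null expectation, and V_k its tie-corrected variance. The plain test ignores strata and uses T ÷ √V. The van Elteren test uses Σ[T_k/(N_k+1)] ÷ √Σ[V_k/(N_k+1)²].

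**4. Results** (4,000 simulated trials per entry, all in %; loss is van Elteren power minus rank-sum power, in points).

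| Strata | b | Variance explained | Type I, rank-sum | Type I, van Elteren | Power, rank-sum | Power, van Elteren | Loss |
|---|---|---|---|---|---|---|---|
| Equal | 0 | 0 | 5.2 | 5.4 | 75.2 | 74.9 | −0.3 |
| Equal | 0.25 | 4.0 | 4.5 | 5.0 | 73.9 | 75.1 | 1.2 |
| Equal | 0.5 | 14.3 | 3.7 | 5.9 | 71.6 | 75.7 | 4.1 |
| Equal | 0.75 | 27.3 | 2.4 | 5.3 | 63.5 | 75.2 | 11.7 |
| Equal | 1 | 40.0 | 1.4 | 4.8 | 54.0 | 75.2 | 21.2 |
| 10/20/70 | 0 | 0 | 5.4 | 5.3 | 75.0 | 75.4 | 0.4 |
| 10/20/70 | 0.25 | 2.7 | 5.4 | 5.7 | 74.6 | 75.8 | 1.2 |
| 10/20/70 | 0.5 | 9.9 | 4.3 | 5.2 | 71.3 | 74.6 | 3.3 |
| 10/20/70 | 0.75 | 19.8 | 2.7 | 4.3 | 67.9 | 75.3 | 7.4 |
| 10/20/70 | 1 | 30.6 | 2.7 | 5.5 | 62.8 | 75.2 | 12.4 |

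The simulation standard error is about 0.7 points for power (√(0.75 × 0.25 ÷ 4000)) and 0.3 points for type I error (√(0.05 × 0.95 ÷ 4000)). The differences at zero variance explained are therefore noise.

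**5. Sensitivity to sample size.** SAP 15.2 uses the FAS for secondary variables, up to 170 subjects are randomised, and missing scores are not imputed (SAP 15.2.1). The number analysed could therefore exceed 128. A run with 170 subjects, equal strata and a shift of 0.43 SD (2,500 trials) showed the same pattern: 76% for both tests at 0% of variance, then 72%, 68% and 60% for rank-sum against 75%, 75% and 74% for the stratified test at 10%, 20% and 30%.

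**The case against.** The strongest reply is that a valid prespecified test is being exchanged for another on grounds of efficiency alone, and that the efficiency gain is undocumented. The scores are changes from baseline, and no section links wound area to those changes. At zero or weak association the tests perform alike. This stands, and it is why the size can only be given as a range that starts at zero.

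Nor is it fair to say that the plan adjusts every other secondary comparison. The log-rank test (SAP 15.2.2) and the wound-closure chi-square test (SAP 15.3) carry no strata either. The plan broadly adjusts its regression models and leaves its simple two-sample tests unadjusted. The log-rank test does have an adjusted companion, and granulation tissue has the mixed model of SAP 16. The other seven scores have neither.

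Three stronger readings are tempting and are not supported:

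- A reader might infer that the trial is throwing away power its sample size was meant to provide. Sample size and power are set for the primary endpoint only (Protocol 6.1.1 and 6.1.2, SAP 5.4).
- A reader might infer that the p-values are invalid. The error is on the conservative side.
- A reader might extend the point with equal force to SAP 15.4. Those are treatment summaries rather than listed efficacy endpoints, and Protocol 5.5.3 already requires the same dressing-change frequency in both groups.

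**Conclusion.** The point holds as a minor efficiency improvement to a valid analysis. The design stratifies by wound area, and the between-arm rank tests of the clinical assessments do not use that. Across the assumed settings the cost runs from nothing to about 21 percentage points of power, and the rank-sum type I error falls from about 5% to as low as 1.4%. The van Elteren test stayed between 4.3% and 5.9%.

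The size depends chiefly on how much of the change-score variance area explains, which the documents do not give. It also rests on the assumed treatment shift, its being common to all strata, and the stratum shares. The direction does not depend on whether the strata are equal or unequal, and no material penalty appeared when area was unrelated to outcome. Neither the non-inferiority test nor the superiority test that follows it uses these scores, so the trial's main conclusion is untouched.

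**What to change.** In SAP 15.2.4, name the van Elteren test as the between-arm test of each change score: a rank-sum test stratified by the three wound-area classes as used at randomisation. In SAS this is a Cochran–Mantel–Haenszel analysis with modified ridit scores. Keep the plain rank-sum test as a sensitivity analysis and leave the within-arm signed-rank tests as they are.

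Because Protocol 6.5.1 also names the rank-sum test, record the change in SAP Section 2, which now reads as not applicable. Protocol 6.6 asks for this when methods change before data lock. Update the output template too, since SAP Section 8 lets the template override the SAP text where they differ. Using the same test in SAP 15.4 is optional.

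The cost is a few lines of SAP text, one template entry and one code option. No new data are needed.

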## **5.5 Study Procedure**

### **5.5.1 Schedule of Activities**

**Schedule of Activities**

Procedures	Screening Day -3~0	Randomization Day 0	Dressing Change Visit (s)	End of Treatment Visit 	Withdrawal or Discontinuation Visit 
Informed Consent	X				
Demographics a	X				
Medical History	X				
Surgical History	X				
Wound History b	X				
Vital Signs c	X				
Physical Exam	X	X	X	X	X
Blood Routine Examination d	X			X	X
Blood Coagulation Function e	X				
Serum Pregnancy Test f	X				
Evaluate inclusion/exclusion criteria	X	X			
Wound Clinical Assessments g		X	X	X	X
Wound Surgical Debridement		X 			
Digital/3D Wound Imaging h		X	X	X	X
Randomization		X			
NPWT		X	X		
Dressing Changes			X		
Concomitant Medications	X	X	X	X	X
AEs/SAEs Review and Evaluation	X	X	X	X	X
Device Deficiencies		X	X	X	X

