5.4. SAMPLE SIZE CALCULATION

The number of evaluable subjects required for this trial is 128 subjects (64 per treatment arm). To account for a potential 10% drop-out rate, at least 140 subjects (70 per treatment arm) will be randomly assigned in a 1:1 allocation ratio to V.A.C. VERAFL™ or control group.

140 evaluable subjects (70 per study arm) will achieve approximately 80% power to detect a difference with a non-inferiority margin of 20% based on a one-sided t test with a significance level of 0.025 and pooled standard deviation being 40%.

Due to the uncertainty in the actual variability and trying to limit the study size to those strictly needed, a sample size re-estimation will be performed after 50% evaluable subjects per arm (70 subjects total) have completed End of Treatment Visit. This number of subjects is expected to provide a sufficiently precise calculation of the variability in the actual study population.

The point estimate for the pooled standard deviation will be used for the sample size re-estimation. If the re-estimated sample size is greater than 140, the sample size may be increased up to a maximum of 200 subjects to provide sufficient power for this study. If the re-estimated sample size is less than 140, the sample size of the study is still 140.

Considering the actual drop-out rate during the clinical trial, the drop-out rate needs to be adjusted from the expected 10% to 25%. The sample size will increase by 30 subjects, to a total of maximum 170 subjects.

170 evaluable subjects (85 per study arm) will achieve approximately 80% power to detect a difference with a non-inferiority margin of 20% based on a one-sided t test with a significance level of 0.025 and pooled standard deviation being 40%.

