7.5. STATISTICAL TESTS

The descriptive statistics of continuous variables include number, mean, standard deviation, median, minimum and maximum. Frequency and percentage will be used in the descriptive statistics for categorical variables. Unless otherwise specified, all statistical tests will be performed at a significance level of 5.0% (two-sided) with two-sided 95% confidence interval (CI).

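### The between-arm tests of the wound clinical assessments subtract the Day 0 score but do not condition on it, which can cost precision

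*SAP*

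**What the plan says.** The Protocol (Secondary and safety endpoints, under 6.5.1) names the method in one sentence: "The Wilcoxon rank-sum test and Wilcoxon signed rank test will be performed for wound clinical assessments". SAP 15.2.4 fills this in. It tabulates "wound clinical assessments change from baseline (change scores from -4 to +4", applies the signed rank test to change within each arm, and applies the rank-sum test to "significant differences in change scores between treatment groups (p-values". No covariate enters either test.

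The Day 0 score is part of the planned data. The Protocol's Schedule of Activities marks the row "Wound Clinical Assessments g" at randomisation, at dressing changes, at End of Treatment and at withdrawal. Protocol 5.5.2.2 repeats it for Day 0: "Wound depth, Edges, necrotic tissue type and amount, granulation tissue, undermining, exudate type and exudate amount will be evaluated". SAP 15.2.4 gives the time points as "Day of Randomization (Day 0), Dressing Change Visit (s), End of Treatment Visit".

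Comparing these assessments between arms is a stated secondary objective (Protocol 4.2, SAP 3.2).

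**The concern.** A change score fixes the slope on baseline at 1. If the true slope is lower, as it is when the scores are measured with error or regress towards the mean, the subtraction adds baseline noise to the comparison. A method that estimates the slope avoids this.

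The scale has only five levels. On necrotic tissue amount, for example, a wound at 1 on Day 0 can only stay the same or worsen, while a wound at 5 can only stay the same or improve. The rank-sum test on change treats the two as exchangeable.

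The SAP adjusts its other main efficacy comparisons for wound-size class and centre: the primary ANCOVA (15.1.3), the Cox model (15.2.2) and the wound area ANCOVA (15.2.3). These items have no adjustment at all. At stake is the chance of detecting a real difference in granulation, necrosis, depth or exudate with data that will be collected anyway.

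**Working it through.** **The plan's own figure.** The only sample size statement concerns the primary endpoint: "The number of evaluable subjects required for this trial is 128 subjects (64 per treatment arm". With margin 20, SD 40 and one-sided alpha 0.025, the noncentral t gives 80.15% power at 64 per arm, so the figure reproduces. No power, effect size, SD or correlation is given for the clinical assessments.

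**Inputs.**
- 64 per arm (SAP 5.4).
- Two-sided 5%, from SAP 7.5: "all statistical tests will be performed at a significance level of 5.0% (two-sided) with two-sided 95% confidence interval (CI".
- Assumed, because the documents give neither: ρ, the correlation between the Day 0 and End of Treatment scores, and k, the ratio of baseline SD to end SD.

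**Variance.** Set the end variance to 1.
- Change score: 1 + k² − 2ρk
- Conditional on baseline: 1 − ρ²
- Difference: (1 + k² − 2ρk) − (1 − ρ²) = (k − ρ)², which is never negative

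So in large samples conditioning never does worse. The proportional cut is (k − ρ)² / (1 + k² − 2ρk). For k = 1 this reduces to (1 − ρ)/2.

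| ρ | Cut, k = 1 | Cut, k = 0.5 |
|---|---|---|
| 0.2 | 0.80/2 = 40% | 1 − 0.96/1.05 = 9% |
| 0.3 | 0.70/2 = 35% | 1 − 0.91/0.95 = 4% |
| 0.5 | 0.50/2 = 25% | 1 − 0.75/0.75 = 0% |
| 0.7 | 0.30/2 = 15% | 1 − 0.51/0.55 = 7% |

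At k = 1 and ρ = 0.8 the cut is 0.20/2 = 10%. The cut is also the share of the sample size that is in effect given up.

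**Power, normal theory, k = 1.** Suppose the effect gives the conditional analysis 80% power at 64 per arm. The change-score test then has power Φ(2.80 × √((1 + ρ)/2) − 1.96):
- ρ = 0.3: Φ(0.30) = 62%
- ρ = 0.5: Φ(0.47) = 68%
- ρ = 0.8: Φ(0.70) = 76%

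**Check on ordinal scores.** These formulas are only a guide for a rank test on five levels, so the comparison was also simulated, with a latent normal variable cut into categories. All cut-points and effects are assumptions.
- *Five levels at both visits, general improvement, 64 per arm.* Rank-sum on change against rank ANCOVA: 51% vs 80% (ρ = 0.2), 57% vs 76% (0.5), 56% vs 68% (0.8). Type I error was near 5% for both.
- *Equal quintiles at both visits, 70 per arm, latent shift 0.45 SD.* 49% vs 71% (0.2), 62% vs 78% (0.5), 80% vs 89% (0.7).
- *Two-level 50/50 baseline, five-level end score, same n and shift.* 69% vs 70% (0.2), 77% vs 78% (0.5), 83% vs 85% (0.7).

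The simulations agree with the algebra: the gain is material when baseline and end spreads are similar, and near nil when the baseline is compressed.

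**The case against.** The strongest reply is that the gain may be small for the items in this trial. Subjects enrol after definitive debridement. Exclusion 12(d) bars necrotic tissue with eschar left in the wound, and exclusion 10 bars undermining or tunnelling of about 15% or more. Baseline scores for necrosis and undermining may therefore be compressed, and the k = 0.5 column shows how little conditioning can then add. This stands for those items. It need not apply to granulation, exudate, edges or depth. The same compression may also put many wounds near the floor, where change scores are least comparable.

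The rank-sum test on change is also a valid, prespecified method, and Protocol and SAP agree on it. These are secondary endpoints for which no power is claimed. Both points stand, and they limit the importance of the concern. Granulation tissue also has an exploratory mixed model (SAP section 16), but that model adjusts for wound-size class and centre, not for baseline granulation.

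A reader might infer that the plan ignores the baseline score. It does not: the score is subtracted. A reader might also infer that the comparison is biased. Randomisation keeps the unadjusted test valid, and simulated type I error was near 5%. A chance imbalance in baseline scores affects the precision of the realised comparison; it is not a systematic error of the plan.

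**Conclusion.** The concern holds as a point about efficiency. The sole between-arm test of these items does not condition on a baseline score that is scheduled for every subject, and in large samples conditioning cannot do worse under the variance model used.

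The size is not known. With equal variances the variance cut runs from 35% at ρ = 0.3 to 10% at ρ = 0.8. With a baseline SD half the end SD it is 0 to 9% for ρ from 0.2 to 0.7. It will differ by item. The tempting statement that these tests lose a large share of their power is not supported, because it needs a correlation and a baseline spread that the documents do not give.

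One uncertainty remains. Protocol 5.5.2.2 lists the Day 0 clinical assessment before definitive debridement. If that order is chronological, the baseline may be a pre-debridement score, which could lower ρ. The documents do not say that the list is chronological.

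The sample size and the primary non-inferiority conclusion are unaffected.

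**What to change.** In SAP 15.2.4, before database lock, replace the between-arm test for each item by a rank ANCOVA: the ranked End of Treatment score, with the ranked Day 0 score as covariate, compared between arms. It may be stratified by the randomisation wound-size classes. Keep the −4 to +4 change table and the within-arm signed rank tests as descriptive output.

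A proportional-odds model with the Day 0 score is an alternative, but it adds an assumption that may be fragile where categories are sparse. Rank ANCOVA is the safer default.

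The cost is a sentence or two of SAP text and a few lines of code. No new data are needed, and no extra subjects are lost, because a change score already requires both values. The small downside is that the tested effect is no longer a simple change score, although the retained table still shows the changes.
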